Statistical Analysis Approach

IRB 10-04957

A video game to enhance cognitive health in older adults, children, and adolescents

“Characterizing the Synergistic Effects of Physical and Cognitive Training on Attention and Working Memory”

May 31 2023

Statistical Analysis Approach:

Analyses were conducted by researchers who were blind to group membership. To test for training effects on each of the collected outcome measures, we used an repeated measures ANOVA approach as in our previous work^{1,2}. Statistically, no between-group differences assessed using independent t-tests were observed for at baseline involving: (1) age ($t_{47}= 0.35$, $p= 0.73$); (2) gender ($t_{47}= -0.15$, $p= 0.88$); (3) CPT performance ($t_{45}= 1.84$, $p= .07$); (4) Filter task performance ($t_{46}= 1.34$, $p= .19$); (5) mft power ($t_{44}= 1.70$, $p= .10$); (6) mft ITC ($t_{41}= 1.11$, $p= .28$); (7) limits of stability ($t_{44}= 1.05$, $p= .30$); (8) diastolic blood pressure ($t_{43}= 1.77$, $p= .08$). For those measures that showed a trend towards a group difference at baseline (CPT performance, mft power, and blood pressure), we performed an analysis of covariance (ANCOVA) with post-training performance as the dependent variable, pre-training performance as the covariate, and group as the fixed factor. Our reasoning for using this approach is that this analysis accounts for variation around the post-test means that arises from the variation where participants began at pretest³. Using this approach, we observed a nearly significant group difference following training for the CPT task ($F_{(1,46)}= 3.85$, $p=0.056$), a significant group effect for mft power ($F_{(1,44)}= 4.35$, $p=0.043$) and a significant group effect for diastolic blood pressure ($F_{(1,42)}= 6.93$, $p=0.012$), supporting the assertion that the reported ANOVA effects were not driven by trending baseline differences between groups. For post-hoc analysis of the within-group changes, we performed two-tailed, paired-sample t-tests on each group separately to test for significant differences between each testing session. We report Cohen's d for all significant ($p< .05$) and trending ($p< .10$) ANOVA results, using the Hedges and Olkin correction⁴ for small sample bias.

References

- 1 Anguera, J. A. *et al.* Video game training enhances cognitive control in older adults. *Nature* **501**, 97-101, doi:nature12486 [pii] 10.1038/nature12486 [doi] (2013).

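### Baseline-adjusted ANCOVA is reported only where a baseline t-test showed a trend, so Filter, theta ITC and limits of stability rest on a change-score test alone despite baseline gaps of 0.31-0.39 SD

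*SAP*

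**What the plan says.** The SAP (Statistical Analysis Approach) sets one method for all outcomes: "To test for training effects on each of the collected outcome measures, we used an repeated measures ANOVA approach". It then states that "no between-group differences assessed using independent t-tests were observed" at baseline and lists eight t-tests, two on age and gender and six on outcomes.

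Three outcomes are then picked out: "For those measures that showed a trend towards a group difference at baseline (CPT performance, mft power, and blood pressure"). For these it fits an ANCOVA with "post-training performance as the dependent variable, pre-training performance as the covariate, and group as the fixed factor". Its stated reason is that this model allows for where each participant started. The ANCOVA is presented as a check, "supporting the assertion that the reported ANOVA effects were not driven by trending baseline differences between groups", so the ANOVA remains the reported analysis for these outcomes too.

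The other three tested outcomes have no reported ANCOVA. Their baseline results are printed as "4) Filter task performance ($t_{46}= 1.34$, $p= .19", "6) mft ITC ($t_{41}= 1.11$, $p= .28" and "7) limits of stability ($t_{44}= 1.05$, $p= .30". The only visible reason for leaving them out is the baseline p-value.

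**The concern.** A baseline t-test in 43-48 people has little ability to detect imbalance. A gap must reach about half a standard deviation before it counts as a trend, so failing to reach that mark does not show that the arms began level. The SAP's own reason for ANCOVA applies just as well to the three outcomes that missed the mark.

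Two things are at stake. With a pre-training and a post-training session, the group-by-session test is a test on change scores. If the arms start apart by chance, part of the difference in change is regression towards the mean. The change-score test also usually has a larger standard error than ANCOVA, which matters in a trial with 24 and 25 people per arm. The assurance that baseline differences did not drive the effects therefore covers only three of the six outcomes tested.

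**Working it through.** **Inputs.** The t statistics, degrees of freedom and p-values come from the SAP; the arm sizes (BBT 24, MBT 25) come from the protocol's Participants section. N = df + 2, split as evenly as possible; other splits allowed by the arm sizes move the gaps by no more than 0.004 SD. The pre/post correlation r is not in the documents, so it is assumed and varied. Pre and post variances are assumed equal. The ANOVA test of interest is taken to be group by session over the pre and post visits.

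**1. The plan's figures reproduce.** Two-sided p from the printed t and df: Filter 0.187, ITC 0.274 (printed .28), limits of stability 0.300, CPT 0.072, theta power 0.096, diastolic pressure 0.084. From the printed F values, the ANCOVA p-values are 0.0558, 0.0428 and 0.0118, against 0.056, 0.043 and 0.012 in the SAP.

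**2. Baseline gaps in SD units**, gap = t x sqrt(1/n1 + 1/n2):
- Filter: 1.34 x sqrt(1/24 + 1/24) = 0.387
- ITC: 1.11 x sqrt(1/21 + 1/22) = 0.339
- Limits of stability: 1.05 x sqrt(1/23 + 1/23) = 0.310

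The same formula gives 0.54 for CPT, 0.50 for theta power and 0.53 for diastolic pressure. A baseline p below .10 needs a gap of about 0.48-0.51 SD at these sizes.

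**3. Offset of the change-score test given the observed gap** = (1-r) x gap, in SD:

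| r | Filter | ITC | Stability |
|---|---|---|---|
| 0.3 | 0.271 | 0.237 | 0.217 |
| 0.5 | 0.194 | 0.170 | 0.155 |
| 0.7 | 0.116 | 0.102 | 0.093 |
| 0.9 | 0.039 | 0.034 | 0.031 |

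The corresponding ANCOVA offset is about zero.

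**4. Precision.** The change-score variance is proportional to 2(1-r). The ANCOVA variance is proportional to (1-r^2), multiplied by a cost for the imbalance of 1 + t^2/df. The ratio of ANCOVA to change-score variance is therefore ((1+r)/2) x (1 + t^2/df).
- Imbalance cost: Filter 1 + 1.34^2/46 = 1.039; ITC 1 + 1.11^2/41 = 1.030; stability 1 + 1.05^2/44 = 1.025.
- At r=0.5: 0.75 x cost = 0.78, 0.77, 0.77.
- At r=0.7: 0.85 x cost = 0.88, 0.88, 0.87.
- Break-even r = 2/cost - 1: Filter 0.92, ITC 0.94, stability 0.95.

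**5. Simulation under no effect** (24 per arm, 200,000 trials for each of r=0.5, 0.7 and 0.8). Over all randomisations the change-score estimate averages zero to within 0.001 SD, with type I error 0.050-0.051. Among trials with a gap near the Filter value, the mean offset is 0.188, 0.112 and 0.075 SD in size, and type I error is 0.066, 0.063 and 0.055. ANCOVA in those same trials has an offset near zero and type I error 0.048-0.054.

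**The case against.** The strongest defence is that the trial is randomised, so the ANOVA is valid as it stands. That is correct: over randomisations it is unbiased with the right type I error. A reader might infer that the three results are simply biased; the documents do not support that. The offset exists only given the observed gap, and even for Filter, the largest, it raises type I error only to about 0.055-0.066 over r=0.8-0.5.

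Other stronger readings also fail.
- *The trigger switches the main model.* It does not. The ANOVA is reported for every outcome and already subtracts baseline; the trigger decides only who gets the extra check.
- *The offset flatters BBT.* The positive t for age matches BBT minus MBT (68.8 against 68.2), which might suggest that BBT began with more variable Filter response times. The SAP states no sign convention and does not say which arm was higher, so the direction is open.
- *The baselines jointly show failed balance.* Fisher's combined p is 0.026 for the six outcomes if they are independent. It is 0.086 over all eight listed comparisons and 0.21 for the three outcomes at issue. Theta power and ITC are related measures, so independence is doubtful. This supports nothing about these three.
- *ANCOVA is always more precise.* It is not, once the imbalance cost is counted (step 4).

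The defence is also right on reach. The protocol calls the Filter task and limits of stability exploratory. ITC is not named there, but it is an EEG measure and neither the primary outcome (CPT) nor the secondary one (working memory).

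What remains is that the check was selective, on a criterion that does not establish balance.

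**Conclusion.** The point holds as a free improvement. Three of the six tested outcomes, with gaps of 0.31-0.39 SD, have only a change-score test because a low-powered baseline test was not near significance. Given those gaps, the test is offset by 0.16-0.19 SD at r=0.5 or 0.09-0.12 SD at r=0.7, and ANCOVA would cut the variance by roughly 22-23% or 12-13% respectively. At r=0.9 the offset shrinks to 0.03-0.04 SD and the precision gain to 1-3%.

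These sizes rest on assumed r, equal pre and post variances and a two-session comparison; with unequal variances, the pre-to-post regression slope replaces r in the offset. No post-training results for the three outcomes are given, so no change of conclusion can be shown and none is claimed.

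**What to change.** Drop the baseline-test trigger. Report the SAP's ANCOVA (post-training value on baseline value and arm) as the between-group analysis for every outcome with a baseline value, whatever its baseline p-value. That means adding Filter, ITC, limits of stability, the exploratory fitness measures and the working memory task, for which the SAP lists neither a baseline test nor an ANCOVA. CPT, theta power and diastolic pressure already have theirs. Because the SAP already contains results, label the added models as specified afterwards.

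Replace the statement that the arms did not differ at baseline with a table of baseline differences in SD units, showing which arm was higher.

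The cost is a few extra models on data already held, one residual degree of freedom per outcome, and the small variance cost of the imbalance (2.5-3.9% for these three).

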91 and other support during the training.

92 All participants reported to our UCSF Neuroscape laboratories prior to training ('Pre-training' session) and  
93 following the completion ('Post-training' session) of training (1-week grace period from start/end of training) to compete  
94 a battery of cognitive and physical outcome measures to assess training-related changes. Participants were invited to  
95 return to the laboratory 1 year after their post-training outcome assessment to evidence which, if any, positive training  
96 effects persisted in the cognitive domain. Over the course of the study, 3 participants in the BBT group and 2  
97 participants in the MBT group voluntarily withdrew from the study, resulting in the complete pre- and post-training data  
98 sets from 24 BBT participants and 25 MBT participants. One additional participant had a non-training related adverse  
99 event which caused them to withdraw from the study prior to be randomized to a group. We were unable to collect EEG  
00 data from three participants at pre-training due to equipment malfunctions, and, due to technical issues with  
01 photodiodes, we were unable to time-lock the EEG to the event onsets for several other participants (n= 4 at pre-  
02 training, n= 4 at post-training). There was one participant who did not return for their post physical assessment.

#### 03

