#### 94 **Neural Cognitive Control Assessments:**

95 *EEG Recordings.* Neurophysiological data were recorded during each cognitive control assessment using an  
96 active two head cap (Cortech Solutions) with a BioSemiActiveTwo 64-channel EEG acquisition system in  
97 conjunction with BioSemiActiView software (Cortech Solutions). Signals were amplified and digitized at 1024 Hz  
98 with a 16-bit resolution. Anti-aliasing filters were used and data were band-pass filtered between 0.01–100 Hz  
99 during data acquisition. For each EEG recording session, a 1 × 1-inch white box was flashed for 10 ms at one of  
00 the corners on the stimulus presentation monitor at the start of each trial. A photodiode  
01 (<http://www.gtec.at/Products/Hardware-and-Accessories/g.TRIGbox-Specs-Features>) captured this change in  
02 luminance to facilitate precise time-locking of the neural activity associated with each sign event. During the  
03 experiment, these corners were covered with tape to prevent participants from being distracted by the flashing  
04 light.

05  
06 *EEG Preprocessing.* Preprocessing was conducted using the EEGLAB software. Noisy channels were identified  
07 upon initial visual inspection, were removed from the data, and interpolated using a spherical spline

08 interpolation, using the average signal of the surrounding channels to reconstruct the data in the removed  
09 channel. The data were then down-sampled to 1024 Hz to reduce the computational demand without losing  
10 any important information in the data. A finite impulse response filter with a high-pass cutoff of 1 Hz was applied  
11 to remove drift, and then a low-pass filter at 40 Hz was applied to remove high frequency noise. Ocular  
12 correction was performed by using ICA to isolate and remove activity induced by eye-blinks and lateral eye  
13 movements from the signal. The data were then re-referenced to the average signal of all channels. Epochs of -  
14 1000 ms to +1000 ms were generated for each stimulus type for subsequent analyses. Epochs containing  
15 excessive peak-to-peak deflections ( $\pm 100 \mu\text{V}$ ) were removed.

16

17 *Midline Frontal Theta Analyses.* Midline frontal theta (4-7Hz) power (mft Power) has been implicated in  
18 sustained attention abilities, including correlating with RTV across the lifespan, that can evidence the  

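### For the primary outcome (CPT) the baseline-adjusted result, p=0.056, is only weak support for the ANOVA effects; ANCOVA was run only where a baseline test trended, and the printed df conflict

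*SAP*

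**What the plan says.** The SAP (Statistical Analysis Approach) names the main method: "To test for training effects on each of the collected outcome measures, we used an repeated measures ANOVA approach". It then lists baseline t-tests and uses them to decide where to adjust. The trigger reads "For those measures that showed a trend towards a group difference at baseline (CPT performance, mft power, and blood pressure". For those three measures it fits an ANCOVA of the post-training value on group and the pre-training value.

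The three adjusted results are:
- CPT: F(1,46)=3.85, p=0.056, introduced with "we observed a nearly significant group difference following training for the CPT task"
- mft power: F(1,44)=4.35, p=0.043
- diastolic blood pressure: F(1,42)=6.93, p=0.012

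One clause draws the same conclusion from all three: "supporting the assertion that the reported ANOVA effects were not driven by trending baseline differences between groups". The SAP attaches the labels p<.05 (significant) and p<.10 (trending) to ANOVA results and sets no separate level for ANCOVA.

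The protocol (Methods, Participants) makes CPT the primary outcome. Its Study Design section reports complete pre- and post-training data "sets from 24 BBT participants and 25 MBT participants", which is 49 people.

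**The concern.** Three things are at issue.

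- **The inference.** The robustness claim treats the primary outcome like the two measures whose adjusted test was below .05. A reader could take the CPT effect to be confirmed after adjustment, when its interval just includes zero.
- **The method.** Adjustment depends on a baseline significance test, so outcomes are analysed in different ways for a reason unrelated to which analysis is better. Neither document says which analysis decides if ANOVA and ANCOVA differ. CPT is where this could matter, because its baseline test trended (t=1.84) and its adjusted p-value is close to .05.
- **The counts.** This ANCOVA needs a pre and a post value for each person, so it cannot include more people than the baseline test of the same measure. For two of the three measures the printed df suggest that it does.

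**Working it through.** **1. Reproducing the printed p-values.** The upper tail of F(1, df) gives:
- CPT, F=3.85 on 46 df: p=0.0558 (printed 0.056; critical F at .05 is 4.05)
- mft power, F=4.35 on 44 df: p=0.0428 (printed 0.043)
- diastolic blood pressure, F=6.93 on 42 df: p=0.0118 (printed 0.012)

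All three agree with the SAP.

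**2. Size of the adjusted CPT difference.** In residual SD units, SE = sqrt(1/n1+1/n2) × sqrt(1+t²/(N-2)), where t=1.84 is the baseline test, and the difference is sqrt(F) × SE.
- With 24 and 25 people: SE = 0.2858 × 1.0354 = 0.2959. The difference is 1.962 × 0.2959 = 0.58. The 95% CI is 0.581 ± 2.013 × 0.2959, or -0.02 to 1.18.
- With 23 and 24 people (an assumed split of 47): 0.59, CI -0.02 to 1.20.

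**3. Could ANOVA and ANCOVA differ for CPT?** The CPT ANOVA is not printed, so this is a scenario. Assume two visits, which makes the group-by-time test a comparison of change scores. Set the pre SD to 1 and the post SD to k, with pre/post correlation r. With 23 and 24 people the baseline gap is 1.84 × 0.2918 = 0.537. The change-score difference is the adjusted difference plus (1 - r·k) × 0.537 if the arm that did better after adjustment started worse, and minus that amount if it started better. The SD of change is sqrt(1 + k² - 2rk).

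Example with r=0.6, k=1:
- The adjusted difference is 0.594 × 0.8 × sqrt(45/44) = 0.480.
- If that arm started worse, the change difference is 0.480 + 0.4 × 0.537 = 0.695. The SD is 0.894, so t = 0.695/(0.894 × 0.2918) = 2.66 and p=0.011.
- If it started better, the same steps give p=0.31.

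Over r = 0.4 to 0.8 and k = 0.8 to 1.2 (assumed ranges), p is about 0.008 to 0.04 if that arm started worse and about 0.06 to 0.80 if it started better.

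**4. Counts implied by the df.** A pooled t-test has N = df + 2. An ANCOVA with two groups and one covariate has N = error df + 3.

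| Measure | Baseline df → N | ANCOVA df → N |
|---|---|---|
| CPT | 45 → 47 | 46 → 49 |
| mft power | 44 → 46 | 44 → 47 |
| Diastolic blood pressure | 43 → 45 | 42 → 45 |

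Blood pressure agrees, so the conversion works there. For CPT, the protocol's 49 complete sets fit the ANCOVA but not the baseline test. Other error df do not repair the table: N - 2 would match mft power (46) but give 48 for CPT and 44 for blood pressure, and N - 4 widens the gaps.

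**5. Effect of the counts with F fixed.** Limiting each ANCOVA to the baseline N gives CPT p=0.0561 on 44 df and mft power p=0.0430 on 43 df. Neither crosses .05.

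**6. Cost of leaving other outcomes on ANOVA.** With equal SDs, the variance of ANCOVA relative to change scores is (1+r)/2: 0.90 at r=0.8 and 0.70 at r=0.4. ANCOVA would have 10 to 30% less variance. This is a matter of precision, not of type I error.

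**The case against.** The SAP asks whether baseline imbalance explains the effects, and p<.05 on the adjusted test is not the only way to answer that. A difference of about 0.58 residual SD after adjustment is some support, and the text prints the p-value with a cautious label. This stands: it would be wrong to strike CPT from the sentence only because 0.056 lies above a line that 0.043 lies below. The sentence needs qualifying.

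Repeated-measures ANOVA is also legitimate in a randomised trial, and moving to ANCOVA after the results are known is a post hoc choice. That is true, and is why the change must be labelled.

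A Welch test could explain the CPT counts. With 24 and 25 people, 45 df arises if the arm SDs differ by a factor of about 1.19 or 1.29, depending on which arm varies more. A factor of about 1.11 could do the same for mft power at 23 and 24, if the smaller arm varies more. The SAP mentions only independent t-tests, so the conflict needs an explanation but need not be an error.

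A reader might infer three stronger things that the documents do not support:
- **That ANOVA and ANCOVA disagree for CPT.** The ANOVA result and the baseline means are not given. The scenario in which that arm started better also fits poorly with a reported ANOVA effect, since p exceeds 0.10 in about 96% of the assumed grid.
- **That the adjusted result shows no effect, or that it was hidden.** The interval is compatible with a sizeable difference, and the p-value is in plain view.
- **That the EEG losses leave only 42 people for mft power (49 - 3 - 4).** This needs all seven pre-training losses to be different members of the 49 and to affect the CPT recording. The protocol says "Neurophysiological data were recorded during each cognitive control assessment", so losses may be specific to a task. The count also leaves out the four post-training losses, and the printed baseline test already implies 46.

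**Conclusion.** The point holds. The CPT ANCOVA (0.58 residual SD, 95% CI about -0.02 to 1.18, p=0.056) is weak and inconclusive support for the robustness claim, and the SAP should not group it without qualification with the other two results. Making adjustment depend on a baseline test is a weaker method than adjusting throughout. Whether the two analyses disagree for CPT cannot be determined. If the arm that did better started worse, ANOVA would fall at about 0.008 to 0.04 while ANCOVA is at 0.056, but this rests on a two-visit ANOVA and the assumed r and SD ratio.

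The df conflict is two people for CPT and one for mft power, reading the baseline tests as pooled and the ANCOVA as stated. It changes no conclusion with F fixed. It matters because F itself could change if the analysed set changes, and mft power is not far below .05.

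Confidence is high for the printed p-values, the missing rule and the df mismatch. The change-score ranges are only illustrative.

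**What to change.** - Use ANCOVA (post on group and pre) for every outcome with a baseline value and remove the baseline-test trigger. Show the repeated-measures ANOVA alongside, name ANCOVA as the deciding analysis, and label the change post hoc.
- Reword the support sentence for CPT: the adjusted result did not reach p<.05 and its CI includes zero. Say that the estimate is in the reported direction only if the data show this.
- Report the adjusted CPT difference with its 95% CI, the CPT ANOVA F and p, and the baseline CPT mean in each arm.
- Print N per arm for every test. Correct or explain the CPT and mft power df, for example by stating that a Welch test was used, and re-run if the analysed set changes.

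The cost is SAP wording and a re-run on data already held. The CPT statement becomes slightly less favourable, and the change of deciding analysis is itself post hoc.

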We have previously demonstrated that cognitive interventions using closed-loop, adaptive algorithms led to target specific cognitive abilities in older adults can improve task performance and neural measures of cognition, with some evidence of these effects persisting well after the intervention period. These interventions, delivered as engaging video games, have shown positive effects not only with older adults, but in diverse populations, with previous work highlighting the possibility of returning performance on measures of cognitive function to young adult level. Here we created a novel exergame intervention for older adults (Body-Brain Trainer, **figure 1**) that requires participants to perform full-body, physical movements in response to cognitive challenges that engage different cognitive control domains. As in our previous work, we integrated real-time adaptivity and closed loop mechanics for each cognitive ability being challenged. Given the movement demands of BBT, we also

12 implemented an adaptive physical fitness challenge by using real-time heart rate data to titrate game play for a  
13 personalized and integrated training experience across both cognitive and physical domains (see **Methods** and  
14 **Supplementary Materials** for more details on the BBT software).

15 In the present study, we sought to evaluate the primary question of whether BBT could improve measures of  
16 attention and physical fitness in older adults beyond that of an expectancy-matched, active placebo control group. To  
17 the best of our knowledge, this design is noteworthy given that the use of expectancy matching has been absent in all  
18 previous efforts examining cognitive benefits from combined approaches, including those studies designed to evidence  
19 potential synergistic effects through mechanistic control groups (see **Supplemental Materials** for a brief treatise  
20 describing our rationale for utilizing this particular control group). We also interrogated the following secondary  
21 questions: what is the neural mechanism underlying positive cognitive effects, do any observed cognitive improvements  
22 persist one year later without booster training sessions, does BBT result in older adults achieving comparable levels to  

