38 examining the distribution of long response times. Several studies have demonstrated a clear advantage of this  
39 measure over traditional measures of response time (although we report on traditional metrics of response  
40 time and response time variance in the **Supplemental Materials**) given that it explains a greater proportion of  
41 variance without needing to employ data trimming techniques. Importantly, this measure has been shown  
42 to reflect performance inconsistencies that are especially present in both healthy older adults and those with

43 mild cognitive impairment, and has been used to support neural noise and dedifferentiation theories  
44 of cognitive aging.

45 For the present study, we adapted the task for use with EEG recordings, which requires many trials with  
46 an actual response, and also facilitates the examination of ex-gaussian tau, a non-parametric measure of  
47 distribution skewing of response times. In this task, participants maintain fixation on a central crosshairs  
48 and grey squares are shown on a black background at the top or bottom of the field of view. Stimuli are  
49 presented frequently at the top of the screen as a 4:1 ratio of targets to nontargets and participants are  
50 instructed to only respond to these stimuli. Participants completed 2 blocks of 125 trials with 100 targets per  
51 block, yielding 200 total targets and 50 non-target trials.

52

53 *Working memory fidelity task.* We used a delayed recognition working memory paradigm designed to measure changes  
54 in participants' ability to maintain an accurate mental representation of items in working memory either in presence or  
55 absence of distracting or interfering information. We have used versions of this task in numerous previous  
56 studies. To summarize briefly, this paradigm consisted of three different conditions that were presented in  
57 blocks: 1) no distraction (ND), 2) Ignore distractor (ID, distractor was present, but participants were informed that the  
58 distractor was to be ignored), and 3) Attend Distractor (AD, participants were required to make a judgment about the  
59 interfering stimulus). Each run was preceded by an instruction slide informing the participant which condition they  

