82 distractors (3 total items), set size 3 with distractors (5 total items). Half of each of the trials for each condition began  
83 with a cue indicating the participant should attend to either the left or the right side of the screen. The procedure for  
84 each trial began with a 750 ms fixation cross following by a right/left cue (200ms) and then a 300 ms blank ISI. Next, a  
85 sample set from one of the four conditions was shown for 200ms followed by a 900 ms blank delay and then a probe set  
86 containing the same number of red rectangles as in the sample in either the same orientation or with a single rectangle  
87 of altered orientation (50% of each). The probe screen remained visible until participants responded with a "Yes" or  
88 "No" button press indicating whether or not one of the attended rectangles changed orientation. Participants  
89 completed 8 blocks of 80 trials, yielding 160 trials per condition. Participants were instructed to respond as fast as  
90 possible without sacrificing accuracy. As in our previous work, we focused on Response Time Variability (RTV) as our  
91 measure of interest here.

92  
93

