### 30 **Physical outcome measures:**

31 To capture changes in physical fitness due to training during the study, all participants underwent a  
32 comprehensive physical outcomes assessment in addition to the cognitive assessments described above. Our  
33 targeted outcome measures were a senior-specific measure of stability indicative of fall risk as well as a  
34 physiological measure of fitness and health (diastolic blood pressure). Our decision to focus on diastolic (rather  
35 than systolic) blood pressure was based on diastolic blood pressure being a proportionally larger contributor to  
36 mean arterial pressure (MAP), with MAP being an important predictor of cardiovascular disease.  
37 Descriptions of each exploratory fitness measure evaluated, including systolic blood pressure, are described in

38 the **Supplemental Materials**; note that these measures came from the Senior Fitness Test (SFT) to assess global  
39 physical performance.

40  
41 **Training-related expectancy ratings:**

42 In an effort to identify an expectancy matched placebo versus the BBT intervention, we first compared  
43 expectancy on 10 different apps to BBT in a sample of 261 participants (Female=135, mean age=33.5). Each  
44 participant was randomly assigned to view a video of BBT or one of 10 potential apps (n= 15–30 individuals  
45 per app) which we did not hypothesize would improve cognitive abilities. They were then asked to rate the  
46 extent to which the presented intervention would lead to improvements on these outcomes, using a Likert  
47 scale measuring 1 (no improvement) to 7 (a lot of improvement). Following this first round of testing, we  
48 selected the three apps that had the highest expectancy matching scores, and subsequently collected new  
49 expectancy data in a sample of 76 young adults to assess the level of expectancy involving the combination of  
50 these three apps (n=37) versus BBT (n=39). Here we found no differences in participant expectations of  
51 improvement on our CPT task ( $t_{74}= 0.24$ ,  $P = 0.62$ , 95% CI: -1.3 to 0.77) or on our filter task ( $t_{74}= 0.55$ ,  $P = 0.16$ ,  
52 95% CI: -0.30 to 1.8), suggesting that we had comparable expectancy on this battery of control apps as  
53 compared to the BBT intervention with respect to our cognitive control outcome measures.

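### The SAP promises Cohen's d only for ANOVA results with p<.10, names no standardiser, and requires no confidence interval for any trial outcome

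*SAP*

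**What the plan says.** The SAP is one analysis paragraph (Statistical Analysis Approach). Its scope is wide: "To test for training effects on each of the collected outcome measures, we used an repeated measures ANOVA approach". For measures with a trend towards a baseline difference (CPT, midline frontal theta power, diastolic blood pressure) it adds an ANCOVA on the post-training score. Within-group changes are examined by paired t-tests.

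Only the closing sentence deals with effect sizes. It promises Cohen's d "for all significant ($p< .05$) and trending ($p< .10$) ANOVA results, using the Hedges and Olkin correction". Nothing is said about effect sizes for ANOVA results at p>=.10, for the ANCOVA or for the paired tests. No standardiser is named, and confidence intervals are not mentioned.

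The ANCOVA results are given as F and p alone; the primary outcome is described as a "nearly significant group difference following training for the CPT task ($F_{(1,46)}= 3.85$, $p=0.056".

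Intervals do appear in the Protocol (Training-related expectancy ratings), for example "95% CI: -1.3 to 0.77". They belong to a separate young-adult survey used to choose the control apps, not to a trial outcome.

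**The concern.** A rule that attaches effect sizes only to results below a p-value cut-off yields a set selected for being large. On average the magnitudes in that set lie further from zero than the true effects. The Hedges and Olkin factor does not help: it removes small-sample bias (about 1.6% at 47 df), not selection.

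The missing intervals are a separate gap, and they affect the results that do get a d. The Protocol (Methods, Participants) says the study gauges feasibility and potential efficacy for a subsequent mechanistic trial. A reader making that judgement needs to know which effects are small, which are null, and how wide the uncertainty is around each. The rule promises the first two only as p-values and the third not at all. Without a standardiser, a reported d also cannot be compared with one from another study.

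**Working it through.** **Inputs.** Arms of 24 and 25 (Protocol, Participants). F statistics and baseline t-tests from the SAP. Assumed, because the documents do not give them: true d, pre-post correlation r, equal pre and post SDs, arm splits per outcome, and that the p<.10 filter acts on the group-by-session term.

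**1. The SAP's own p-values.** The upper tail of F gives F(1,46)=3.85: 0.0558; F(1,44)=4.35: 0.0428; F(1,42)=6.93: 0.0118. These match the printed 0.056, 0.043 and 0.012.

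**2. Smallest d that gets reported.** With two sessions, the group-by-session test is a t-test on change scores with 47 df.
- Threshold = J × t(.95, 47) × sqrt(1/24 + 1/25) × sqrt(2(1-r)), with J = 1 - 3/(4×47 - 1) = 0.984.
- At r=.5 the last factor is 1, which is the same as scaling on the SD of change: 0.984 × 1.678 × 0.2858 = 0.47.
- On the raw SD: 0.30 at r=.8 and 0.21 at r=.9. These are typical values rather than hard floors.

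**3. Selection at p<.10, SD of change** (2,000,000 noncentral-t draws per row, signed means, Hedges-corrected):

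| True d | Share reported | Mean reported d | Ratio |
|---|---|---|---|
| 0.1 | 12% | 0.38 | 3.8 |
| 0.2 | 18% | 0.57 | 2.8 |
| 0.3 | 27% | 0.64 | 2.1 |
| 0.5 | 53% | 0.72 | 1.4 |
| 0.8 | 87% | 0.87 | 1.1 |

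At a true d of 0 the signed mean stays at 0, but mean |d| is 0.60 among reported results against 0.23 without selection.

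**4. The same, raw SD.** At r=.8 the ratios are 1.5 (d 0.3), 1.1 (0.5) and 1.00 (0.8). At r=.9 they are 1.2 (0.3) and 1.01 (0.5). A given d on the raw SD is not the same effect as that d on the SD of change, which is why the standardiser matters.

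**5. What an interval would add for the printed results.** d = J × sqrt(F) × sqrt((1/n1 + 1/n2)(1 + tb²/dfb)), where tb and dfb come from the baseline t-test; limits by inverting the noncentral t. Signs are not printed, so these are magnitudes, in ANCOVA residual SD units.
- CPT (24 v 25; tb 1.84 on 45 df; J 0.984): 0.984 × 1.962 × 0.2963 = 0.57, 95% CI -0.01 to 1.15.
- Midline frontal theta power (23 v 24; tb 1.70 on 44 df): 0.62, 0.02 to 1.21.
- Diastolic blood pressure (22 v 23; tb 1.77 on 43 df): 0.80, 0.18 to 1.41.

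To express the CPT upper limit in raw post-training SDs, multiply by sqrt(1 - r²): 1.152 × 0.866 = 1.00 at r=.5, × 0.600 = 0.69 at r=.8, × 0.436 = 0.50 at r=.9.

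**6. A conflict in the inputs.** The CPT baseline t on 45 df implies 47 people, while a one-covariate ANCOVA with 46 error df implies 49. For theta power the figures are 46 and 47. The effect here is small: CPT at 23 v 24 gives 0.58 (-0.02 to 1.18).

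**7. A null outcome.** At 24 v 25, an estimate of exactly zero would still carry about ±0.55.

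**The case against.** The strongest reply is that no harm is shown, and that stands. The SAP guarantees d for some results; it does not say that others are withheld. It refers to reported ANOVA effects that are not printed in it, and the Protocol points to Supplemental Materials that are not available here. All three printed between-group results have p<.10, though they are ANCOVA results and the rule concerns ANOVA. Where F, df and arm sizes are printed, a reader can recover d and an interval, as above. A reader might infer that null findings were suppressed; the documents do not support that.

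The rule also speaks of ANOVA results, not outcomes. An outcome with a null interaction but a significant session effect would still receive a d, so it is not established that any outcome goes without one.

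Two readings of the numbers go too far. One is that the CPT interval reaches beyond 1 SD without qualification: that holds on the residual SD, but not on the raw SD at an r of .5 or higher. The other is that a particular d from this study is inflated: selection biases the reported set on average and cannot be shown for a single estimate.

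What remains is that the plan, as written, requires neither the unselected effects nor any measure of precision.

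**Conclusion.** The point holds as a reporting defect that should be corrected; no printed result is shown to be wrong. The SAP's one effect-size rule is conditional on p<.10, leaves the standardiser open, and requires no interval for any trial outcome.

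The size of the selection effect depends on quantities the documents do not give. Over the values tried it runs from none (raw SD, r=.8, true d 0.8) to about 3.8-fold (SD of change, true d 0.1), and the ratio has no ceiling as the true effect approaches zero. The missing intervals matter even if selection is discounted: the primary CPT result is compatible with anything from about no effect to a large one in residual SD units, and a d alone would not show that.

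A reader might infer that these d values are meant to size the next trial. The documents say only that potential efficacy is to be gauged.

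**What to change.** Replace the last sentence of the SAP with:

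> For every between-group training effect tested, whatever its p-value, we report the estimate (group-by-session difference in change, or the baseline-adjusted difference where ANCOVA is used) and the Hedges-corrected d with its standardiser stated, each with a 95% CI; any 1-year between-group contrast that is analysed is reported in the same way.

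The last clause is limited to contrasts that are analysed. The Protocol (Study Design) invites participants to "return to the laboratory 1 year after their post-training outcome assessment to evidence which, if any, positive training" effects persisted, but the SAP specifies no 1-year between-group test, and this change should not create one.

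When the intervals are produced, state the number analysed per arm for each outcome, since the printed df for CPT and theta power disagree.

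The cost is a longer results table and more cautious wording of imprecise findings. For effects already tested, no new data are needed.
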